9.1 Extent of Exposure

The frequency distribution of the number of subjects will be calculated for each number of days of administration. Descriptive statistics will be calculated for the number of days of IMP administration.

9.2 Adverse Events

All AEs will be coded by system organ class and MedDRA preferred term. The incidence of the following events will be summarized by treatment group:

- Treatment-emergent AEs (TEAEs)
- TEAEs by severity
- TEAEs with an outcome of death
- Serious TEAEs
- TEAEs leading to discontinuation of the IMP

If the same event occurs more than once in the same subject, the higher severity will be used. TEAEs related to the IMP will be tabulated similarly.

TEAEs by time of first onset will be tabulated into the following categories.

- Category 1
 - From the start of IMP administration to Day 3 of the treatment period
 - From Day 4 to Day 7 of the treatment period
 - From Day 8 to Day 14 of the treatment period
 - From 1 day after to 2 days after the final IMP administration (including 1 day after and 2 days after the final IMP administration for discontinuation and early completion)
 - More than 2 days after the final IMP administration
- Category 2
 - 1 to 3 days after the start of IMP administration
 - 4 to 7 days after the start of IMP administration
 - 8 to 16 days after the start of IMP administration
 - 17 or more days after the start of IMP administration

9.3 Clinical Laboratory Data

Clinical laboratory values measured at the central laboratory will be used. For clinical laboratory tests other than the qualitative urinalysis, the descriptive statistics of the actual values and changes from baseline at each time point and at the last assessment time point (the day after IMP administration; the same applies hereinafter) will be calculated. A shift table of parameters for the qualitative urinalysis from baseline at each time point and the final time point of the assessment will be prepared. Parameters other than those for the qualitative urinalysis will be categorized based on the reference range into “within normal,” “below the lower limit of normal,” and “above the upper limit of normal,” and a

shift table of each parameter at baseline, each time point after IMP administration, and the last assessment time point will be prepared.

For each item other than the qualitative urinalysis, scatter diagrams of the values at the last assessment against the baseline will be prepared.

Serum electrolyte (K) will also be tabulated, excluding samples with hemolysis of 3+ or higher.

The number and percentage of subjects in which AST or ALT increased to 3 times the upper limit of normal or more and total bilirubin increased to 2 times the upper limit of normal or more at any point after IMP administration will be calculated.

9.4 Vital Sign Data

For vital signs, descriptive statistics of the actual values and changes from baseline at each time point and the last assessment time point will be calculated.

For subjects with a baseline systolic blood pressure of at least 90 mmHg, the number and percentage of subjects who have an actual value of “< 90 mmHg” at least once in each visit from the time after IMP administration to the last assessment time point will be calculated. Similarly, the abovementioned numbers and percentages of subjects will be calculated at each time point after IMP administration.

9.5 Physical Examination Data

No tabulation will be performed.

9.6 Electrocardiogram Data

For 12-lead ECG parameters, descriptive statistics of the actual values and changes from baseline at each time point and at the last assessment time point will be calculated.

For QTc interval (QTcF), respective numbers and percentages of subjects who showed an actual value of “> 450 ms,” “> 480 ms,” and “> 500 ms” at least once in the visits from each time after IMP administration to the last assessment time point will be calculated. In addition, respective numbers and percentages of subjects who showed a change from baseline of “> 30 ms” and “> 60 ms” at least once in the visits from the time after IMP administration to the last assessment time point will be calculated. Similarly, the above mentioned numbers and percentages of subjects will be calculated at baseline and each time point after IMP administration.

A shift table showing normal/abnormal judgment at baseline, each time point after IMP administration, and the last assessment time point will be prepared.

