7.2 Demographic and Baseline Characteristics

For the full analysis set and the safety analysis set Table 7.2-1, descriptive statistics (number of subjects, mean, standard deviation, minimum, median, maximum; the same applies hereinafter up to Section 9) or frequency distribution (number of subjects, %; the same applies hereinafter) will be tabulated.

Table 7.2-1 Demographic and Baseline Characteristics			
Item	Timing	Method	Level
Age (years)	Time of informed consent	Descriptive statistics	–
		Frequency distribution	18-29, 30-39, 40-49, 50-59, 60-69, 70-79, 80-85, 86-89
			<65, ≥65
Sex	–	Frequency distribution	Female, Male
Height (cm)	Screening	Descriptive statistics	–
Weight (kg)	Screening	Descriptive statistics	–
BMI (kg/m ²)	Screening	Descriptive statistics	–
Country where the trial is conducted	–	Frequency distribution	JAPAN
Race	–	Frequency distribution	Asian, American Indian or Alaska Native, Black or African American, Native Hawaiian or Other Pacific Islander, White, Other

Table 7.2-1 Demographic and Baseline Characteristics			
Item	Timing	Method	Level
Ethnicity	–	Frequency distribution	Not Hispanic or Latino, Hispanic or Latino, Unknown
Underlying disease (multiple choice) 
 • Ischemic heart disease • Cardiomyopathy • Valvular disease • Hypertensive heart disease • Arrhythmia 	Screening	Frequency distribution	Yes, No
Heart failure type	Screening	Frequency distribution	Right Heart Failure, Left Heart Failure, Bi-ventricular Failure, Unspecified
Presence or absence of arrhythmia	Screening	Frequency distribution	Yes, No
Presence or absence of pacemaker	Screening	Frequency distribution	Yes, No
Presence or absence of implantable cardioverter defibrillator	Screening	Frequency distribution	Yes, No
Complication (multiple choice) 
 • Hypertension • Angina pectoris • Diabetes mellitus • Renal impairment 	Screening	Frequency distribution	Yes, No
Presence or absence of complications	Screening	Frequency distribution	Yes, No
Presence or absence of medical history	Screening	Frequency distribution	Yes, No

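### The QTcF threshold counts in SAP 9.6 ignore baseline, so they mix existing with new prolongation and dilute arm differences, and no planned summary table shows new crossings (minor)

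*SAP*

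**What the plan says.** SAP 9.6 plans five kinds of ECG summary, which section 9 sets by treatment group in the safety analysis set:

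- QTcF threshold counts: subjects above 450, 480 and 500 ms "at least once in the visits from each time after IMP administration to the last assessment time point will be calculated". No baseline condition is attached.
- Change counts for QTcF: "respective numbers and percentages of subjects who showed a change from baseline of" more than 30 ms and more than 60 ms.
- The same counts by time point: "Similarly, the above mentioned numbers and percentages of subjects will be calculated at baseline and each time point after IMP administration".
- Continuous summaries: "For 12-lead ECG parameters, descriptive statistics of the actual values and changes from baseline at each time point" and at the last assessment.
- A qualitative shift table: "A shift table showing normal/abnormal judgment at baseline, each time point after IMP administration, and the last assessment time point will be prepared".

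For the systolic pressure count (<90 mmHg), SAP 9.4 does set a baseline condition: "For subjects with a baseline systolic blood pressure of at least 90 mmHg, the number and percentage of subjects who have an actual value" below the limit after dosing.

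Appendix 1 lists two categorical ECG summary tables: CT-12.2 (normal/abnormal shift) and CT-12.3 (categorical changes). Individual ECG results are listed in PDATA-6.1 and PDATA-6.2.

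**The concern.** A subject at 465 ms before the first dose and 465 ms throughout treatment is counted as >450 ms after dosing, exactly like a subject who moves from 430 to 465 ms. Only the second tells the reader anything about the drug. The SAP recognises this for systolic pressure and gives no reason for treating QTcF differently.

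Baseline prolongation is a reasonable worry here. All subjects have congestive heart failure, and Table 7.2-1 provides for cardiomyopathy, arrhythmia, implantable defibrillator and "Presence or absence of pacemaker" as baseline items. That table lists items to be tabulated, however, and says nothing about how common they are.

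At stake is how clearly the categorical QT table can be read with 31 subjects per arm. Subjects prolonged before dosing add the same expected background to every arm. That background shrinks the visible difference in new prolongation and adds chance noise.

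**Working it through.** **1. Can new crossings be recovered from the other planned summaries?**

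- *Baseline threshold counts.* These are separate margins. Suppose an arm has 8/31 above a threshold at baseline and 10/31 at least once after dosing. New crossings could be as few as 10 − 8 = 2 (all eight stay above) or as many as 10 (none of the eight is above again).
- *Change counts.* These do not identify crossings. A move from 475 to 502 ms crosses both 480 and 500 ms with a change of 27 ms, below the 30 ms cut-off. A move from 400 to 435 ms counts as >30 ms and crosses nothing.
- *Shift table.* It covers only the normal/abnormal judgment, not QTcF categories.
- *Listings.* They allow reconstruction subject by subject, but they are not a summary by arm.

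So no listed summary table gives the number who newly exceed each threshold.

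**2. How much does the missing condition dilute a difference?**

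The SAP has no QTcF figure to reproduce. The only document input is n = 31 per group (SAP 4). That figure is itself consistent: a two-sample t-test with difference 1.09, SD 1.30 and two-sided 5% has power 0.901 at n = 31.

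Let b be the share above the threshold at baseline, r the probability that such a subject is above it at least once after dosing, and q the new-onset rate among the rest. The planned count estimates

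p = b·r + (1 − b)·q.

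If r is the same in both arms, the between-arm difference is (1 − b)(q₁ − q₀). The illustration assumes r = 1, q₀ = 5% on placebo and q₁ = 20% on drug. The difference among subjects not above the threshold at baseline is then 15 points.

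| b (assumed) | Placebo count | Drug count | Difference | Already above, share of drug-arm count |
|---|---|---|---|---|
| 5% | 0.05 + 0.95×0.05 = 9.75% | 0.05 + 0.95×0.20 = 24% | 14.25 points | 0.05/0.24 = 21% |
| 20% | 0.20 + 0.80×0.05 = 24% | 0.20 + 0.80×0.20 = 36% | 12.0 points | 0.20/0.36 = 56% |
| 50% | 0.50 + 0.50×0.05 = 52.5% | 0.50 + 0.50×0.20 = 60% | 7.5 points | 0.50/0.60 = 83% |

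The SAP plans no test on this table, so power serves only as a yardstick for readability. By the normal approximation for two proportions (two-sided 5%), the unrestricted count with 31 per arm compares with the restricted count with 31(1 − b) per arm as follows:

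- b = 5%: 0.32 against 0.41
- b = 20%: 0.174 against 0.355
- b = 50%: 0.09 against 0.24

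In these cases, removing the background gains more than the smaller denominator loses.

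**3. Chance imbalance at baseline.**

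The 95% range of the difference in baseline share between two arms of 31 is ±1.96·√(2b(1 − b)/31). This gives ±11 points at b = 5%, ±20 at b = 20% and ±25 at b = 50%. At b = 1% to 6%, it is ±5 to ±12 points.

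**The case against.** The case against making much of this is strong, and most of it stands.

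*Tempting reading 1: the counts cannot show a drug effect.* The documents do not support this. The trial is randomised and placebo-controlled (SAP 3.1) and the tables are by arm, so baseline prevalence is balanced in expectation. A difference is attenuated but does not vanish: in the illustration 7.5 points remain even at 50% prevalence.

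*Tempting reading 2: the counts consist largely of subjects already prolonged.* The SAP gives no baseline QTcF distribution, and any QTc eligibility limit would be in the protocol, which is not at hand. The answer depends on what is assumed. A simulation without drug effect used mean 430–450 ms, between-subject SD 28, within-subject SD 10–15 and 3–5 post-dose ECGs. It puts the already-above share at 53–77% of the >450 ms count, about 34–60% for >480 ms and about 24–50% for >500 ms. With mean 415 ms and SD 22, the share for >450 ms falls to about 33–45%. A majority at every threshold is therefore not established.

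*Tempting reading 3: an imbalance would pass for a signal.* Baseline counts by arm are planned, so an imbalance would be visible. Ranges of ±20 to ±25 points arise only if 20–50% of subjects are above the threshold at baseline, which is implausible for >500 ms under the simulated settings (about 1–6%).

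Further, 9.6 already refers each subject to their own baseline through the >30 and >60 ms counts and the mean changes. Section 9.4 has no baseline or change-category counts for systolic pressure, so the two sections are different approaches rather than a contradiction.

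What remains is narrow: the absolute counts mix two groups, and no planned summary table separates them.

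**Conclusion.** The point holds as a minor one. The QTcF threshold counts in 9.6 take no account of baseline, unlike the systolic pressure count in 9.4, and the other planned ECG summaries do not recover the number newly crossing each threshold.

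The size is a dilution by about (1 − b). It is negligible if few subjects are above the threshold at baseline (15 points becomes 14.25 at b = 5%) and substantial if many are (7.5 at b = 50%). The factor assumes that subjects already above the threshold are above it again equally often in both arms. The values of b and of the new-onset rates are assumptions, not document figures. The effect is likely to matter most at >450 ms and least at >500 ms.

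This is a cheap improvement to a descriptive safety table. It corrects no error that would invalidate the QT assessment.

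**What to change.** Keep the planned absolute counts and the >30 and >60 ms change counts. Replacing the absolute counts would remove subjects already prolonged at baseline from them, which is unnecessary. Add to 9.6 and CT-12.3, by treatment group:

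- (a) for each of 450, 480 and 500 ms, the number and percentage newly exceeding the threshold at least once after dosing, among subjects at or below it at baseline, following the form that 9.4 uses for systolic pressure;
- (b) a cross-tabulation of baseline QTcF category (≤450, >450–480, >480–500, >500 ms) by highest post-dose category.

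The cost is a sentence or two in 9.6 and one more table, with no new data. The downside is a smaller denominator for the treatment-emergent counts, which the cross-tabulation makes visible. The change is best made before unblinding.

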9.7 Other Safety Data

Not applicable.

10 Pharmacokinetic Analyses

The following analyses will be performed in the PK analysis set.

10.1 Endpoints

- 1) Plasma concentrations of OPC-131461, M35101, and M35103 (Day 1 to Day 16)
- 2) Plasma pharmacokinetic parameters for OPC-131461, M35101, and M35103
 - Day 1
 C_{max} , AUC_{24h} , t_{max} , t_{last} , C_{max}/D , AUC_{24h}/D
 - Day 7
 C_{max} , AUC_{24h} , t_{max} , t_{last} , C_{max}/D , AUC_{24h}/D
 - Day 14
 C_{max} , AUC_{24h} , t_{max} , $t_{1/2,z}$, $CL/F^{#1}$, $CL/F/BW^{#1}$, t_{last} , λ_z , C_{max}/D , AUC_{24h}/D
#1: Not calculated for metabolites
- 3) Ratio of the AUC_{24h} of M35101 or M35103 to that of OPC-131461 (Day 1, Day 7, and Day 14)
- 4) Cumulative for OPC-131461, M35101, and M35103 (Day 7 and Day 14)
 - $R(C_{max})$, $R(AUC_{24h})$, and $R(C_{trough})$
- 5) Dose proportionality of the C_{max} and AUC_{24h} of OPC-131461 (Day 1, Day 7, and Day 14)

10.2 Statistical Methods

- 1) Data on each of the endpoints presented in [Section 10.1 1](#)) will be summarized by compound, treatment group, and day of IMP administration. In addition, data on the endpoints shown in [Section 10.1 1](#)) will be summarized by time point of blood sampling, while data on the endpoints shown in [Section 10.1 2\), 3\), and 4\)](#) will be summarized by parameter. The descriptive statistics to be calculated will include the number of subjects in the analysis set, number of subjects tabulated, arithmetic mean, standard deviation, coefficient of variation, and minimum, median, and maximum values for plasma drug concentration, and the number of subjects in the analysis set, number of subjects tabulated, arithmetic mean, standard deviation, coefficient of variation, geometric mean, and minimum, median, and maximum values for PK parameters. For t_{max} and t_{last} , the arithmetic mean, standard deviation, coefficient of variation, and geometric mean will not be calculated. For λ_z , descriptive statistics will not be calculated.

2) For the endpoints shown in [Section 10.1 5](#)), data will be analyzed by day of IMP administration using regression equation (I) to obtain an estimate of b and its two-sided 95% CI.

$$\ln Y = a + b \cdot \ln X \dots (I)$$

X: Dose

Y: Parameter (C_{\max} and AUC_{24h})

The parameter will be determined to show dose proportionality when the two-sided 95% CI of the estimate of b includes 1.

[figure not shown]
3) For each compound in [Section 10.1 1](#)), a graph comparing changes in blood concentration between treatment groups by day of IMP administration and a graph comparing changes in blood concentration between day of IMP administration by treatment group will be prepared on a linear scale (mean \pm SD and median) and a logarithmic scale (mean and median). In addition, a graph of the blood concentration versus time profile (spaghetti plot) for all subjects by day of IMP administration and treatment group will be prepared for each compound, and a comparative graph of the blood concentration versus time between administration days by treatment group will be prepared for each compound and subject, both on an actual value scale and a logarithmic scale. For trough concentrations, a comparison graph of blood concentrations between treatment groups will be prepared for each compound on an actual value scale (mean \pm SD and median) and a logarithmic scale (mean and median). In addition, a graph of trough concentrations versus time profile (spaghetti plot) will be prepared for each compound and all subjects by treatment group. The C_{\max}/D and AUC_{24h}/D of the unchanged drug in [Section 10.1 2](#)) will be plotted against dose for each day of IMP administration. The relationship graph will plot the individual values and mean \pm standard deviation with the C_{\max}/D or AUC_{24h}/D of the same treatment group as the vertical axis (Y-axis) and the treatment group as the horizontal axis (X-axis).

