During the treatment period, subjects will orally receive the IMP once daily for 14 days. However, the treatment will be terminated before completing 14 days of treatment, if the investigator or subinvestigator judges that no further improvement of volume overload is necessary in a case that all congestive findings present at baseline are resolved or in other cases. Subjects who complete the trial or who discontinue the trial after receiving the IMP will undergo the end-of-treatment (EOT) examination on the day after the final IMP administration, post-treatment examination 2 days after the final IMP administration, and follow-up examination 10 to 14 days after the final IMP administration. Subjects will also be followed up for AEs, as necessary.

All subjects should undergo EOT/withdrawal examination, post-treatment observation, and follow-up after the final IMP administration even if the actual treatment duration is less than 14 days as specified in the protocol.

The trial duration for each subject is from informed consent to the end of the follow-up examination.

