3.4 Handling of Time Points

Efficacy, safety, and exploratory endpoints will be described (see [Section 11.2](#) for baseline pharmacodynamic endpoints).

The analysis visit used for tabulating each visit will be the CRF visit and time point values. Follow-up examinations for pharmacokinetic endpoints and pharmacodynamic endpoints will not be tabulated. However, the completion/discontinuation test visits will be classified into the following analysis visits.

- End-of-treatment examination in subjects who completed 14-day IMP administration: Day 15
- End-of-treatment examination in early completers: Visit on the applicable day (excluding congestive findings, chest X-ray [cardiothoracic ratio, pulmonary congestion], NYHA classification, and 12-lead ECG [Because these items, which are specified to be measured at a feasible time after IMP administration, are measured after IMP administration during treatment, while for early completers, IMP will not be administered the next day.])
- Withdrawal Examination: Visit at discontinuation (not tabulated as visit of discontinuation)

Post-treatment observation will be classified as Day 16 for patients who have completed 14 days of IMP administration (however, post-treatment observation analysis visits will also be prepared for items other than PK and PD endpoints).

Echocardiography will be classified as “Day 15-16” if it is assessed at the completion/discontinuation test visit or post-treatment observation.

For pulmonary congestion, cardiothoracic ratio, and NYHA classification, if IMP is administered for less than 7 days, the day after IMP administration will be included in the analysis visit “Last assessment by Day 7 (day of IMP administration).”

The baseline of each item is defined as follows.

Table 3.4-1 **Handling of Time Points**

*If there are multiple data in the run-in period, the data closest to Day 1 will be adopted as the baseline.

4 Sample Size

The sample size is set as 31 subjects per group.

Assuming that a dose of OPC-131461 at 5 mg or higher is equivalent to 15 mg of tolvaptan in patients with CHF, the sample size required to demonstrate the superiority of OPC-131461 over placebo in terms of the primary endpoint, ie, the change in body weight from baseline to the last assessment time point (the day after IMP administration) by Day 8, was determined (multiplicity relating to the use of more than one OPC-131461 dose group was not considered).

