5.3 PK Analysis Set

Includes all subjects who have been administered at least one OPC-131461 and have at least one measurement of plasma drug concentration.

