PKT-6.2 Individual and Summary of M35101 Plasma Pharmacokinetic Parameters Following Multiple Oral Administration of OPC-131461 (Day 7) (Pharmacokinetics Analysis Set)

PKT-6.3 Individual and Summary of M35103 Plasma Pharmacokinetic Parameters Following Multiple Oral Administration of OPC-131461 (Day 7) (Pharmacokinetics Analysis Set)

PKT-7.1 Individual and Summary of OPC-131461 Plasma Pharmacokinetic Parameters Following Multiple Oral Administration of OPC-131461 (Day 14) (Pharmacokinetics Analysis Set)

PKT-7.2 Individual and Summary of M35101 Plasma Pharmacokinetic Parameters Following Multiple Oral Administration of OPC-131461 (Day 14) (Pharmacokinetics Analysis Set)

PKT-7.3 Individual and Summary of M35103 Plasma Pharmacokinetic Parameters Following Multiple Oral Administration of OPC-131461 (Day 14) (Pharmacokinetics Analysis Set)

PKT-8.1 Individual and Summary of OPC-131461 Plasma Accumulation Parameters Following Multiple Oral Administration of OPC-131461 (Pharmacokinetics Analysis Set)

PKT-8.2 Individual and Summary of M35101 Plasma Accumulation Parameters Following Multiple Oral Administration of OPC-131461 (Pharmacokinetics Analysis Set)

PKT-8.3 Individual and Summary of M35103 Plasma Accumulation Parameters Following Multiple Oral Administration of OPC-131461 (Pharmacokinetics Analysis Set)

PKT-9 Dose Proportionality of OPC-131461 Pharmacokinetic Parameters (Pharmacokinetics Analysis Set)

PKF-1.1 Mean OPC-131461 Plasma Concentrations Following Single Oral Administration of OPC-131461 (Pharmacokinetics Analysis Set)

PKF-1.2 Mean M35101 Plasma Concentrations Following Single Oral Administration of OPC-131461 (Pharmacokinetics Analysis Set)

PKF-1.3 Mean M35103 Plasma Concentrations Following Single Oral Administration of OPC-131461 (Pharmacokinetics Analysis Set)

PKF-2.1 Median OPC-131461 Plasma Concentrations Following Single Oral Administration of OPC-131461 (Pharmacokinetics Analysis Set)

PKF-2.2 Median M35101 Plasma Concentrations Following Single Oral Administration of OPC-131461 (Pharmacokinetics Analysis Set)

PKF-2.3 Median M35103 Plasma Concentrations Following Single Oral Administration of OPC-131461 (Pharmacokinetics Analysis Set)

PKF-3.1 Individual OPC-131461 Plasma Concentrations Following Single Oral Administration of OPC-131461 (Pharmacokinetics Analysis Set)

PKF-3.2 Individual M35101 Plasma Concentrations Following Single Oral Administration of OPC-131461 (Pharmacokinetics Analysis Set)

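### The dose-proportionality rule in SAP Section 10.2 treats failure to reject b = 1 as proof of proportionality, so imprecise data favour a false positive conclusion

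*SAP*

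**What the plan says.** SAP Section 10.1, item 5), lists dose proportionality of Cmax and AUC24h of the parent drug on Days 1, 7 and 14 as a PK endpoint. Section 10.2, item 2), fits ln Y = a + b·ln X separately by day, with X the dose, "to obtain an estimate of b and its two-sided 95% CI". It then gives the decision rule: "The parameter will be determined to show dose proportionality when the two-sided 95% CI of the estimate of b includes 1". Two parameters on three days make six such verdicts.

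The visible text gives no acceptance range for b, no maximum interval width and no minimum number of evaluable subjects. Section 10.3 is redacted and a figure after the rule is not shown, but the decision sentence is complete and refers to neither.

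Section 10.2, item 3), adds plots of dose-normalised Cmax and AUC24h against dose, and Appendix 1 lists "PKT-9 Dose Proportionality of OPC-131461 Pharmacokinetic Parameters". No decision is tied to either.

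**The concern.** The rule is the acceptance region of a two-sided 5% test of b = 1. Failing to reject that hypothesis can mean that the slope is close to 1, or that the data cannot tell. The SAP gives both cases the same positive label. For any true slope other than 1, more variable data or fewer evaluable profiles raise the chance of a wrong proportional verdict, towards 95%. Very precise data have the opposite effect and can reject a trivial departure.

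The number of evaluable profiles may also differ by day. Section 3.1 provides that "the treatment will be terminated before completing 14 days of treatment" in certain cases, and Section 5.5 rules out imputation. The rate of early termination is not given. If it is material, Day 14 would have the fewest profiles and so the most lenient test, and the six verdicts would not be comparable.

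The stakes are limited. This is a PK conclusion under a secondary objective. The primary body-weight analysis, the sample size and the efficacy dose-response contrasts do not use it.

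**Working it through.** **Inputs from the SAP.** Active doses are 1, 2, 5 and 10 mg (Section 3.2); placebo cannot enter a model in log dose. The planned arm size is 31 (Section 4). The interval is two-sided 95% (Section 10.2).

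**Assumptions.** The SAP gives no between-subject CV and no evaluable number per arm. CV is taken as 30%, 50%, 70% and 100%. Evaluable n per arm is 31 (as planned), or 20 or 12 as illustrative losses.

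**The plan's own figure.** The only sizing figure is for body weight (difference 1.09 kg, SD 1.30 kg, 90% power, two-sided 5%). The normal approximation gives 2 × (1.960 + 1.282)² × 1.30² / 1.09² ≈ 29.9. The two-sample t calculation gives 30.9, so 31 is reproduced, with power 90.1%. Nothing was sized for dose proportionality.

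**Precision of b.**
- Log doses are 0, 0.693, 1.609 and 2.303, with mean 1.151. Their squared deviations sum to 1.325 + 0.210 + 0.210 + 1.325 ≈ 3.071 for one subject in each arm.
- σ = √ln(1 + CV²), SE(b) = σ / √(3.071·n), and df = 4n − 2.
- Example: CV 50% gives σ = 0.472. With n = 31, SE(b) = 0.472 / √95.2 = 0.0484 on 122 df, so the half-width is 1.980 × 0.0484 = 0.096.

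**Chance of a proportional verdict** (noncentral t with noncentrality (b − 1)/SE):

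| True b | n per arm | CV 30% | CV 50% | CV 70% | CV 100% |
|---|---|---|---|---|---|
| 1.0 | any | 95% | 95% | 95% | 95% |
| 0.90 | 31 | 9% | 46% | 67% | 79% |
| 0.90 | 20 | 25% | 63% | 77% | 85% |
| 1.2 | 31 | <0.1% | 1.6% | 13% | 36% |
| 1.2 | 20 | <0.1% | 9% | 31% | 54% |
| 1.2 | 12 | 1.8% | 29% | 53% | 70% |

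Over the tenfold range, the dose-normalised exposure ratio of 10 mg to 1 mg is 10^(b−1). This is 0.79 for b = 0.90 and 1.58 for b = 1.2. Simulation with 20,000 runs agrees: for b = 1.2 at CV 50/70/100% it gives 1.5/13.6/35.5% with n = 31 and 28.9/52.5/70.3% with n = 12.

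**What a passing interval can contain.** An interval centred exactly on 1 has these half-widths:
- n = 31: 0.096/0.128/0.169 at CV 50/70/100%, still compatible with 10 mg to 1 mg ratios up to 1.25/1.34/1.48.
- n = 12: 0.157/0.209/0.276, compatible with ratios up to 1.43/1.62/1.89.

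**The converse fault.** At CV 30% and n = 31, a true slope of 1.05 (10^0.05 = 1.12, a 12% drift over the whole range) is rejected 38% of the time.

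**The case against.** The strongest reply has four parts.

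- **The large error rates rest on assumed inputs.** At the only documented arm size and CV 50%, b = 1.2 is wrongly passed in 1.6% of trials, and at CV 30% almost never. Twelve per arm means losing 61% of each arm ((31 − 12)/31), which nothing in the SAP suggests. This stands for large departures. It does not remove the problem for moderate ones: b = 0.90 is passed in 46% of trials at CV 50% with no data loss. The documents do not say whether a 21% drift matters, and without a stated limit the verdict has no defined meaning.

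- **Sparse data are not demonstrated.** The PK set criterion, under which subjects "have at least one measurement of plasma drug concentration", only sets inclusion and does not show that Cmax or AUC24h will be missing. Evaluability rules may lie in the redacted Section 10.3, and early stopping cannot thin Day 1. This is fair, so data loss should be read as a possible aggravation. The fault does not depend on it.

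- **Readers will see b, its interval and the dose-normalised plots.** They will, and that limits the harm. The label is nevertheless fixed by the decision sentence, which ignores interval width.

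- **Equivalence limits carry their own cost.** They can fail a truly proportional drug or, if wide, accept a real drift. This also stands, and it is why limits are offered only as an option.

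**Conclusion.** The concern holds. As written, Section 10.2 turns the absence of a significant departure from b = 1 into a positive determination, and nothing visible in the SAP repairs it. That conclusion follows from the wording and needs no assumption about variability.

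Its practical size does depend on assumed CVs. At the planned 31 per arm, departures of about 20% over the tenfold range are missed in roughly half to two thirds of trials at CVs of 50% to 70%. Departures of about 60% are mostly detected unless CV is high or profiles are lost.

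The sentence should be corrected before analysis. The effect is confined to six secondary PK verdicts.

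**What to change.** Delete the decision sentence in Section 10.2, item 2). Keep the planned estimate of b and its 95% interval, and add to PKT-9 the implied 10 mg to 1 mg ratio of dose-normalised exposure, 10^(b−1), with its interval. Describe an interval containing 1 only as no evidence against proportionality. The cost is one SAP sentence and one derived quantity.

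If the sponsor wants a positive conclusion, it should set limits for b, with a rationale, before unblinding. Proportionality would be declared only when the 90% interval lies wholly inside them; otherwise the result would be called inconclusive. The choice of limits matters. The ranges below are assumed examples, not recommendations. They are 1 ± log10(r) for r = 1.25, 1.5 and 2, evaluated at n = 31:

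| Limits for b | Exposure ratio accepted | Pass rate at b = 1, CV 50/70/100% |
|---|---|---|
| 0.903–1.097 | 0.80–1.25 | 27 / 0.2 / 0% |
| 0.824–1.176 | 0.67–1.50 | 95 / 71 / 32% |
| 0.699–1.301 | 0.50–2.00 | about 100 / 99.7 / 94% |

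The widest limits would also pass b = 1.2 in 67/46/32% of trials, because they accept up to a twofold drift.
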